### 1.0 Study Overview

Fecal incontinence (FI) is very common: 3% of US adults report that it occurs at least weekly. It often has a devastating impact on quality of life and may lead to premature admission to a nursing home. In August 2013, the National Institute of Diabetes, Digestive and Kidney Diseases (NIDDK) invited leaders in the field to a workshop to develop a clinical research agenda for FI. Overwhelmingly, participants identified biofeedback, sacral nerve electrical stimulation, and perianal injection of an inert bulking agent as potentially useful treatments but felt that a critical barrier to progress is the lack of consistent evidence from well-designed, randomized controlled trials (RCTs) regarding their efficacy. The workshop identified trials comparing the effectiveness, safety, and costs of these treatments as the highest priority for research funding. Our goal is to address this significant gap in knowledge by conducting a multisite study comparing the effectiveness, safety, and costs of these treatment (FIT) study, approximately 285 people with moderate to severe FI will be enrolled in this multi-site study. All participants will first be treated with 4 weeks of Enhanced Medical Management (EMM), and 194 who do not respond to EMM will be randomized to the two interventions, Biofeedback (BIO) or injections of Dextranomer bulking agent (INJ). Three months thereafter, non-responders (less than a 75% reduction in FI episodes) may choose to undergo a different (i.e., a second) intervention from the 3 options of BIO, INJ, or Sacral Nerve Stimulation (SNS).

Our specific aims are as follows:

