### 1.1 Specific Aims

- A. Compare the effectiveness, safety, and cost of two treatments for moderate to severe FI in 194 male and female patients in a multi-center RCT; the interventions are biofeedback therapy (5 required weekly sessions with the option of an additional 6th visit, as needed) and perianal injection of the inert bulking agent dextranomer (INJ; Solesta). A ≥75% reduction in average weekly FI episodes compared to baseline will define a responder. The primary efficacy analysis will occur 3 months following the start of each treatment, with long-term follow-up through 2 years. Secondary outcomes will include a validated FI severity scale, a disease-specific quality of life scale, and measures of psychological distress.
  - Research objective 1 (primary). For the primary test of efficacy, the null hypothesis is that the proportion of responders in the two treatment groups will not be different. Secondary analyses will test for equivalence at other time points (e.g., 6, 12 and 24 months follow up) and will compare treatment groups on other secondary outcome measures.
  - Research objective 2 (primary). For the primary test of safety, the null hypothesis is that at 3 months follow up, the proportion of patients with adverse events (AEs) of pelvic pain of grade II or higher based on Common Terminology Criteria for AE (CTCAE) criteria, treatment site infection, or SAEs requiring hospitalization will not be different in the BIO or INJ groups. Secondary analyses will evaluate this outcome at 6, 12, 18, and 24 months follow up.
  - Research objective 3 (primary). At 3 months follow up, the estimated average cost for enhanced medical management non-responders will not be different for the two treatments. Secondary analyses will evaluate this outcome at 6, 12, 18, and 24 months.
- B. Compare efficacy in patients who complete all assigned treatment visits. Efficacy may be influenced by the number of BIO treatment sessions and the requirements to learn and practice new skills. Thus, in a secondary analysis, the primary efficacy outcome will be compared between treatment groups in the subset of participants who completed the treatment to which they were randomized.

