  - INJ will include a preparation for treatment and a treatment visit. Preparation will include the use of enemas and minimal restrictions on food intake. Prophylactic antibiotics should be started on the day of the procedure, per the treatment SOP. On the day of the procedure, a physician will inject 1 ml of dextranomer into each of 4 quadrants of the rectum proximal to the dentate line. Ten seconds will be allowed to pass before the injection needle is withdrawn to minimize drainage of the dextranomer. The patient will be scheduled to return in 6 weeks for possible repeat injection of a second 4 ml of dextranomer. At this second appointment, if FI has improved by 75% or more compared to baseline, the patient will be continued without a second injection. However, if the rate of FI is greater than 75% of baseline, the patient will be offered a second injection of dextranomer.
- 4. Combination therapy: The primary assessment of efficacy is at 3 months following the first treatment visit completed, and patients who have not achieved at least a 75% reduction in FI frequency compared to baseline will be classified as treatment failures; they will be invited to choose either the treatment to which they were not randomized or SNS as an adjunctive treatment for the remaining months of the study. One reason for offering non-responders an opportunity to try an additional treatment is to increase the likelihood that patients will consent to be randomized despite possibly having a priori preferences for one of the two treatments. The assumption that this will increase willingness to be enrolled was confirmed in the pilot feasibility survey we performed in 187 patients with FI representing the clinical sites: 57% of patients reported that the ability to receive the treatment of their choice if the assigned treatment was not effective, was important to their willingness to be randomized. Moreover, the estimated 46% of patients who do add a second treatment after the 3 months primary assessment will enable us to collect exploratory data on the possible benefits of combining these treatments. (None of the two investigational treatments can be discontinued.) Thus, the patients

Figure 1. Study Design

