Previous studies have identified a number of limitations to paper diaries: (1) Missing data if subjects forget to complete the diary or if it is illegible. (2) Inaccurate data that may result if subjects forget to record events when they occur and then try to remember what happened at the end of the day or several days later. In previous studies, we provided patients with a pocket-sized paper diary to take with them throughout the day and asked them to transfer their symptom ratings from the paper diary to a website at the end of the day. If they failed to submit a report to the website within 12 hours, they were sent an email reminder or were telephoned. They were also reminded the next time they attempted to enter data, if the data for the previous day was missing, and they were given an opportunity to report on the previous day; however, they were not permitted to go back further than the previous 24 hours. They were also provided with bonus payments for not missing any diary reports. With this combination of techniques, we were able to obtain an average of 73 consecutive days of symptom diaries without interruption from 185 IBS patients varying in age from 18 to 84. However, there is concern that since advancing age is a risk factor for FI, the patients who enroll in this study will be older and less comfortable than young or middle-aged subjects with transferring data to the internet. Therefore, to avoid biasing enrollment against these older subjects, we decided to use paper diaries for this study. To ameliorate potential problems with missing or untimely data reporting we will (1) thoroughly train subjects in recording their diary information at enrollment, and (2) telephone subjects during the first two weeks that they keep the diary to ensure that they are able to record events on this paper diary when they occur.

To protect against experimenter bias, patients will be classified as responders or non-responders based on diary data entered into the electronic data capture (EDC) system at the end of EMM and at 3-, 6-, 12-, and 24-month follow-up. Once the diary data are entered, a calculation performed within the EDC system will determine which patients are non-responders eligible for randomization, and the same process will determine which patients are non-responders at 3 months so they can be offered alternative treatment.

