#### 5.1 Inclusion/ Exclusion criteria

Inclusion Criteria	Exclusion Criteria
Physician diagnosis of FI (R15) for the past 6 months or longer. We will recruit some subjects by advertisement who may not have consulted a physician, and this diagnosis may be made by the study physician. Able to ambulate independently on level surfaces. Patient may use	Dementia will be assessed using the Six-Item Screener to Identify Cognitive Impairment. The subject is asked to remember 3 words (apple, table, penny), which may be repeated up to 3 times. This is followed by 3 questions on the year, month, and day of the week. Finally, the subject is asked to recall the three words. Three or more errors has a sensitivity of 88.7% and specificity of 88.0% compared to clinical diagnosis and is not different from the Mini Mental State Exam. [Callahan, CM et al. Six-Item Screener to Identify Cognitive Impairment among Potential Subjects for Clinical Research. Medical Care 2002;40:771-81.] Obstetrical injuries including third and fourth degree tears in the anal sphincter within 6 months.
assistive devices other than parallel bars.	
Average ≥2 solid, liquid, or staining FI episodes per week by self-report and during the two-week baseline	Pregnant or planning pregnancy in next 2 years
Meets criteria for dextranomer treatment except an internal anal sphincter defect of 180 degrees or less is acceptable.	Internal anal sphincter separation >180 degrees on ultrasound or magnetic resonance imaging
Required for randomization: Less than 75% reduction in the number of FI episodes after 4 weeks of EMM.	Spinal cord injury or spina bifida
Age >=18 years	Congenital malformation of anorectum
	Complete rectal prolapse or grade III/IV hemorrhoids
	History of ileoanal pouch; history of anal sphincteroplasty, rectopexy, or rectocele repair within the past 6 months; or history of pelvic surgery with synthetic graft and suspected graft erosion into the anus, rectum, or skin or if the graft ends less than approximately 1" above the upper limit of the anal canal.
	Established diagnosis of inflammatory bowel disease
	Intestinal stoma present
	History of pelvic radiation within previous 12 months or presence of active radiation proctitis.
	Patients who cannot expel the rectal balloon during the balloon expulsion test and who have constipation most of the time.
	Anatomic limitations to placement of dextranomer injections.
	Presence of existing implant in the anorectal region

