*6.3 INJ of dextranomer:* This protocol is a modified version of the protocol used by Graf to ensure consistency across sites and safety of patients. Patients are treated prophylactically with oral antibiotics to minimize injection site infections. One ml of NASHA dextranomer is injected through an anoscope into each quadrant of the submucosa (4 ml total) approximately 5 mm above the dentate line. After each INJ, the needle is left in place for 10 seconds to avoid backward leakage of contrast through the injection channel. Following the INJ patients are counselled to use stool softeners (docusate sodium) until the first bowel movement and to use paracetamol as needed for INJ site discomfort. Prophylactic antibiotics will be administered for 2 days starting on the day of injection. Six weeks after initial INJ, patients return for evaluation, and if the patient has achieved less than 75% reduction in FI, a second INJ is given.

6.4 Comparison of elements of BIO and INJ:

Table 9 shows the elements of the two treatments compared to each	h other.
	rouior.

	Enhanced Medical Management	Biofeedback	Injection
Preparation	None	None	Diet restrictions; enemas; and antibiotics per the procedure SOP
Number of visits	2 visit + 2 phone calls	5-6 visits	2 visits
Visit duration	60 min 1 st visit; 15 min phone calls (Day 3; Day 14); 30 min last visit	60 min	45 min
Visit frequency	1 st and last visits (start of treatment and after treatment program has ended)	Up to 2 visits per week, spaced 2-10 days apart for first 5-6 weeks or so	0 and 6 weeks
Procedure	Daily sphincter exercises, meds to normalize bowel habits	Learn how to improve strength and rectal sensation	Bulking agent injected into rectal wall to narrow opening
Expected Adverse Events	None	None	Pain at injection site, bleeding, infection

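### Section 3.0 sets the six-week re-injection threshold at the wrong value, so it conflicts with Section 6.3 and gives no rule for 25% to <75% improvement

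*Combined protocol and SAP*

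**What the plan says.** Two current sections of the protocol state the six-week rule for INJ.

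- **Section 3.0, item 3.** After the first 4 ml: "The patient will be scheduled to return in 6 weeks for possible repeat injection of a second 4 ml of dextranomer". The branch without re-injection is: "if FI has improved by 75% or more compared to baseline, the patient will be continued without a second injection". The branch with re-injection is: "However, if the rate of FI is greater than 75% of baseline, the patient will be offered a second injection of dextranomer".
- **Section 6.3.** At the same visit: "if the patient has achieved less than 75% reduction in FI, a second INJ is given".

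Elsewhere the protocol uses a 75% reduction as its cut-off:

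- Section 1.1 defines response: "A ≥75% reduction in average weekly FI episodes compared to baseline will define a responder".
- Section 1.0 describes those offered another treatment at 3 months as "non-responders (less than a 75% reduction in FI episodes").
- Section 5.1 requires for randomisation: "Less than 75% reduction in the number of FI episodes after 4 weeks of EMM".

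**The concern.** The two branches in Section 3.0 are on different scales. The first uses percent improvement and the second uses percent of baseline remaining. At a cut of 75% these are not complements, so the two sentences leave out the middle of the range. Section 6.3 re-injects everyone in that middle range.

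This is a treatment rule that acts before all three primary endpoints are measured:

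- **Efficacy:** it sets the dose received before the 3-month responder assessment.
- **Safety:** the primary composite counts pelvic pain of grade II or higher and treatment-site infection, and Table 9 lists pain and infection among the expected events for INJ.
- **Cost:** each injection is costed separately in Section 5.2.3.

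The documents describe no automatic safeguard at week 6. Section 4.1.1 says that responder status is computed from "diary data entered into the electronic data capture (EDC) system at the end of EMM and at 3-, 6-, 12-, and 24-month follow-up", a list without the six-week visit. Neither schedule of assessments has a six-week column. Section 3.1 gives the visit a window but no threshold. As far as these documents show, the decision therefore rests on the written rule, and that rule is stated in two ways.

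**Working it through.** **1. Put both rules on one scale.** Let improvement = 1 − (six-week FI rate ÷ baseline rate).

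- Section 3.0, no second injection: improvement ≥ 75%, i.e. rate ≤ 25% of baseline.
- Section 3.0, second injection offered: rate > 75% of baseline, i.e. improvement < 25%.
- Section 6.3, second injection given: improvement < 75%, i.e. rate > 25% of baseline.

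| Improvement at week 6 | Section 3.0 | Section 6.3 |
|---|---|---|
| ≥ 75% | none | none |
| 25% to < 75% | no instruction | second injection |
| < 25% | second injection | second injection |

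Exactly 25% improvement falls in the gap, because Section 3.0 requires a rate strictly above 75% of baseline.

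**2. Translate to diary counts.** Section 5.1 requires an average of at least 2 episodes per week, so the minimum is 4 in the two-week baseline. I assume a two-week count at week 6 as well. The baselines of 8 and 20 are illustrative.

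| Baseline, two weeks | No injection (both sections) | Section 3.0 silent, Section 6.3 re-injects | Second injection (both sections) |
|---|---|---|---|
| 4 | 0–1 | 2–3 | 4 or more |
| 8 | 0–2 | 3–6 | 7 or more |
| 20 | 0–5 | 6–15 | 16 or more |

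**3. Dose at stake.** Four quadrants × 1 ml = 4 ml; with the second 4 ml the total is 8 ml.

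**4. Cost at stake.** Section 5.2.3 gives $281.03 (physician) + $4,900 (device) = $5,181.03 per injection. Two injections come to $10,362.06, which reproduces the $10,363 in Table 5 to within a dollar.

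**5. Does it threaten cost power?** Take the extreme case of one injection for everyone, with the plan's convention that the SD is half the range.

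- INJ: mean $5,181.03; SD = 0.5 × (337.23 − 224.82) + 0.5 × (6,860 − 2,940) = $2,016.2.
- BIO: mean 3 × 265.45 = $796.35; SD = 3 × 0.5 × (318.55 − 212.36) = $159.3.
- Difference: $4,384.7.
- At 97 per arm: SE = √[(2,016.2² + 159.3²)/97] = $205.4, so z = 4,384.7/205.4 = 21.4.
- At the expected 3-month completers (78 BIO, 92 INJ): z = 20.8.

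Power is 1.0 in both cases, so the plan's cost-power statement does not depend on which rule is followed.

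**6. Could the gap hold a material number of people?** The documents give no distribution of improvement at week 6. Table 3 reports that in the pivotal INJ trial 53% had at least a 50% decrease and 32% at least a 75% decrease. The difference, 53% − 32% = 21%, lies between 50% and <75%, inside the gap. These are not week-6 data. They show that the band need not be sparsely populated, but they do not estimate how many would fall in it here.

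**7. Check the fix.** If Section 3.0 said a rate above 25% of baseline, its branches would be ≤ 25% and > 25%. That covers every outcome and uses the same cut as Section 6.3.

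**The case against.** The strongest reply is that this is an editorial slip with a clear intended meaning. Section 6.3, in the chapter on intervention details, states a complete rule. In Section 3.0 the second branch is introduced as the opposite of the first, so a sensible reader would supply the complement. Table 9 (INJ visits at 0 and 6 weeks) and the costing assumption of two injections each also fit routine re-injection short of response. Sites work from procedure manuals and an injection SOP, which may state the rule correctly. Section 3.1 does schedule the six-week visit. No effect on type I error, power, sample size or the validity of the intention-to-treat comparison has been shown, and the diary-count examples only restate the wording arithmetic. Treatments and visits are already collected for the cost analysis, which largely covers whether a second injection was given.

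Most of this stands. The intent is clear, Section 6.3 is complete, practice may already be right, and the number of participants mishandled is unknown. What does not follow is that the sentence can stay. It is current protocol text, it governs dose before the primary endpoints, and the number in it is wrong. The scheduled visit in Section 3.1 carries no threshold that would resolve the conflict. A protocol should not depend on a separate SOP to override its own treatment rule. The change from *given* to *offered* in Section 6.3 and the recording of the week-6 reduction are minor additions and could be dropped without affecting the main correction.

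**Conclusion.** The concern holds. The threshold in Section 3.0 is wrong as written: it is 75% of baseline where the protocol's own logic calls for 25% of baseline. The two sections differ across the whole band from 25% to just under 75% improvement, and a site reading Section 3.0 alone has no instruction there. The consequence is 4 ml or 8 ml of dextranomer and about $5,181 in payer cost for each participant affected. How many would be affected cannot be determined from the documents.

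The conclusion on the wording needs no assumption. The diary-count examples assume a two-week count at week 6. The practical consequence depends on the injection SOP, which is not among the documents. The slip does not bias the randomised comparison. If sites read the rule differently, it would alter which INJ regimen that comparison evaluates. It should be fixed, but it does not threaten the trial's inference.

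**What to change.** In Section 3.0, item 3, replace the re-injection condition with wording such as: *if FI has fallen by less than 75% from baseline (a rate above 25% of baseline), a second injection is offered.* Then:

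- Use *offered* in Section 6.3 too, so that both sections describe the same action.
- Confirm that the injection SOP uses the same cut.
- Record the week-6 percent reduction, derived from the diary that Section 4.1.1 already has participants keep through the intervention period, and whether a second injection was given. If enrolment is well advanced, this record will show which rule sites actually followed.

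The cost is one phrase, one word, an SOP check and one derived field. No change to sample size or to the primary analysis is needed.

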Graf reported there were 128 adverse events and two serious adverse events (AEs) in the 136 patients who received INJ. However, many of these were minor AEs related to changes in stool consistency. The incidence of more significant AEs, such as pain, fever, and/or abscess, was 9.6%. Other investigators have reported comparable rates of AEs in uncontrolled case series. Dextranomer treatment is not consistently reimbursed by third party payers but is estimated to cost approximately \$7,408 if two injections are given

2.2.3. Sacral Nerve Stimulation: SNS is performed in two steps: (1) During test stimulation, a temporary electrode is inserted with its tip near the sacral nerve and connected to an external stimulator for 1-2 weeks. However, screening procedures are evolving, with many surgeons now preferring to use barbed leads intended for permanent implant during the screening stage, reasoning that 70% to 90% of patients will improve enough to warrant a permanent implant, and for these patients, the permanent lead is already in place. In this study, we plan to use the tined lead to avoid the need for a second test if the PNE fails. (2) If FI frequency decreases by at least 50% during PNE, a battery-operated electrical stimulator is permanently implanted beneath the skin. An estimated 10% - 30% of patients fail to meet criteria for permanent implant. Publications on the effectiveness of SNS often report only the outcomes for patients receiving permanent implants, but this makes these outcomes not comparable to reports on BIO and INJ where the analysis sample includes all patients randomized to treatment (intent-to-treat analysis). Consequently, in the literature review below, we adjust for the number of patients failing test stimulation and report the intention-to-treat (ITT) outcomes for SNS.

Although SNS is regarded as standard of care for patients with severe FI who have failed enhanced medical treatment and is approved by the FDA for this indication, few RCTs have been published. Wexner reported a large, uncontrolled multisite study, and this carefully done study was used for our sample size calculations. This study included 133 patients with at least two episodes of solid or liquid FI per week at baseline. After correction for patients who failed the test stimulation, the proportion achieving a 50% reduction by ITT analysis was 71.4% at six months and 66.2% at 12 months.

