who add a second treatment and continue to be monitored up to 24 months will constitute a pragmatic clinical trial (i.e., the study design for these patients going forward emulates the clinical situation in which patients who have an unsatisfactory response to a treatment are offered a new treatment or an ancillary treatment). If SNS is selected as an adjunctive treatment it will be performed as follows:

- SNS will include insertion of a barbed stimulating electrode into the region of the S3-S4 nerve and connection to an external, battery-operated electrical stimulator for 10-14 days to test for reductions in FI. If the rate of FI decreases to at least 50% of the baseline rate, a permanent stimulator will be implanted beneath the skin. The patient will be scheduled to return in 4 weeks for an evaluation of the stimulator settings with adjustment if needed. If the initial 2-week test stimulation shows less than a 50% reduction in FI compared to baseline, SNS will be judged ineffective. The stimulator electrode may be removed at the patient's request or left in place.
- 5. Primary outcomes include safety and cost as well as symptom reduction: Very few studies have compared different treatments for FI (see Section 2.0), and these few have compared treatments based only on reductions in frequency of FI. Data on safety and cost as well as symptom reduction are needed to develop treatment algorithms and reimbursement policies. This study addresses this need by including number and type of adverse events and cost of care for two of the most frequently employed treatments for moderate to severe FI, in addition to reductions in FI. The primary outcomes will be assessed at 3 months following treatment initiation. The window for the 3-month follow-up assessment is 1 week before and 3 weeks after the anticipated due date.
- 6. *Long-term follow-up:* An intention-to-treat analysis of efficacy will be carried out at 6, 12 and 24 months. For these analyses, all patients randomized to the treatment will be included in the analysis. These follow-up assessments should occur within the following windows:
  - 6- and 12-month follow-up assessments 1 week before and 3 weeks after the anticipated due date; and
  - 24-month assessment 3 weeks before and 3 weeks after the anticipated due date.

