#### 5.4 Estimated patient flow for this study

Figure 3 shows the estimated flow of patients through this study and identifies our assumptions regarding attrition. We estimate we will need to screen 855 patients because 2/3 will be ineligible or unwilling to be randomized. This leaves 285 to be recruited into the EMM protocol. Based on the Heymen study, we assume

15% attrition during this treatment phase and also assume that 20% (n=57) will be responders to EMM and therefore not eligible for randomization. This will leave 194 to be randomized (97 per group).

Figure 3 shows that we expect 78 from the BIO group to complete the 3-month assessment after allowing for attrition of 20% and we expect 92 from the INJ group to complete the 3-month assessment. (We assume attrition will be no greater than 5% for the INJ group because this is a low-burden treatment and also because patients will want to be screened for AEs related to INJ.) However, the statistical analysis will be by intent to treat (ITT) and will include all 194 randomized to treatment; patients who are lost to follow up prior to 3 months will be considered treatment failures. The number of patients we expect to be responders to each of the treatments at the 3-month assessment is based on the pivotal trials shown in Table 1. We separated them in this way in Figure 3 to be able to estimate the numbers of non-responders who are likely to choose an additional treatment option after 3 months. The expected number of non-responders eligible for an additional therapy at 3 months is 63 for the INJ arm^16 and 17 for the biofeedback arm^15. Assuming equal probability of choosing either of the 2 available options as an added or alternative treatment, we could expect 40 patients to choose the SNS treatment, 32 to choose BIO, and 9 to choose INJ. For the primary analyses of follow up at 6, 12 and 24 months, these non-responders will be retained in the ITT analysis as non-responders to their primary assignment at randomization. However, when we perform exploratory analyses of treatment combinations, these subjects will be treated as distinct groups and compared to patients who received monotherapy for the duration of the study. These comparisons (Aim D) are exploratory because there is insufficient power to test for significance. The left column of boxes in Figure 3 shows how we intend to follow up the responders to EMM.

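### The permanent SNS implant threshold in section 3.0 is worded as percent of baseline, while the companion sentence and section 2.2.3 use percent reduction; the wording is ambiguous and needs reconciling

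*Combined protocol and SAP*

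**What the plan says.** SNS is no longer a randomized arm. Non-responders at the 3-month assessment may choose it as an added treatment. Section 3.0 item 4 describes a temporary test-stimulation period and then gives two conditions in the same bullet.

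- Implant sentence: "If the rate of FI decreases to at least 50% of the baseline rate, a permanent stimulator will be implanted beneath the skin".
- Ineffective sentence, two sentences later: "If the initial 2-week test stimulation shows less than a 50% reduction in FI compared to baseline, SNS will be judged ineffective".

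Section 2.2.3 describes the same two-step procedure and puts the condition this way: "If FI frequency decreases by at least 50% during PNE, a battery-operated electrical stimulator is permanently implanted beneath the skin". It adds: "An estimated 10% - 30% of patients fail to meet criteria for permanent implant".

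On scale and use, section 5.4 says "we could expect 40 patients to choose the SNS treatment", and of the analyses that use these participants: "These comparisons (Aim D) are exploratory because there is insufficient power to test for significance".

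**The concern.** The implant sentence speaks of what the rate decreases *to*, as a share of baseline. The other two statements speak of what it decreases *by*. With *at least* attached, the first form literally sets a floor on the remaining rate, whereas the others set a floor on the reduction. A site applying the words as printed could find both conditions met for one participant and the implant condition unmet for another who improved much more.

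The sentence governs a permanent surgical implant, and item 4 is where the protocol text states the operative rule: section 6 has subsections for EMM, BIO and INJ but none for SNS. If sites read it differently, the care given to SNS choosers would differ between sites. So would the later response, safety and cost data described by treatment combination.

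**Working it through.** There is no power or sample-size figure to reproduce here; the check is a decision table.

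**Inputs.** The two sentences in section 3.0 item 4; the condition in section 2.2.3; 63 INJ and 17 BIO non-responders, with equal probability of choosing either available option (section 5.4); a 10% to 30% failure rate (section 2.2.3). The baseline of 10 episodes per week is illustrative.

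**Definitions.** Share of baseline = test rate / 10. Reduction = 1 − share.

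- Implant sentence, literal: the rate falls and share ≥ 50%.
- Implant sentence, idiomatic (down to half or lower): share ≤ 50%.
- Ineffective sentence: reduction < 50%.
- Section 2.2.3: implant if reduction ≥ 50%.

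| Test rate per week | Share | Reduction | Implant sentence, literal | Implant sentence, idiomatic | Ineffective sentence | Section 2.2.3 |
|---|---|---|---|---|---|---|
| 10 | 100% | 0% | not met | not met | ineffective | not met |
| 9 | 90% | 10% | **met** | not met | **ineffective** | not met |
| 7 | 70% | 30% | **met** | not met | **ineffective** | not met |
| 6 | 60% | 40% | **met** | not met | **ineffective** | not met |
| 5 | 50% | 50% | met | met | not ineffective | met |
| 4 | 40% | 60% | **not met** | met | not ineffective | met |
| 2 | 20% | 80% | **not met** | met | not ineffective | met |
| 0 | 0% | 100% | **not met** | met | not ineffective | met |

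**Literal reading.**

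1. Reductions above 0% and below 50%: the implant and ineffective sentences both apply, so the decisions are opposite.
2. Reductions above 50%: the implant sentence does not apply and the ineffective sentence is silent. This is a gap in coverage, because neither sentence says *only if*.
3. Exactly 50%, or no decrease: no conflict.

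**Idiomatic reading.** The implant sentence, the ineffective sentence and section 2.2.3 agree in every row.

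**Scale.** Expected SNS choosers: (63 + 17) / 2 = 40. Falling short of the implant criterion: 40 × 0.10 = 4 to 40 × 0.30 = 12. Meeting it: 40 − 12 = 28 to 40 − 4 = 36. The 4 to 12 include anyone with no decrease, for whom the sentences agree, so that range is an upper limit on how many would face opposite decisions under the literal reading.

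**The case against.** The strongest reply is that nobody would apply the literal reading. The bullet presents the test period as a check for reductions in FI, the neighboring sentence is on the reduction scale, and section 2.2.3 is unambiguous. Literally applied, the rule would implant those who barely changed and pass over those who became continent. This stands in part: it shows that the text can be read coherently, and it rules out calling this an unconditional contradiction.

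It does not make the wording safe. The reader must borrow from the background section to settle an operative rule. The same mixing of scales occurs in item 3 of section 3.0, where no idiom helps. There a second injection is withheld at an improvement of 75% or more (25% of baseline or less) but offered when the rate exceeds 75% of baseline, so a participant between those points is covered by neither statement. Section 6.3 words that condition as a reduction of less than 75%. Sites therefore cannot assume that a percent of baseline always stands for a percent reduction.

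A second reply is that section 6.0 refers to detailed procedure manuals, and one may state the SNS criterion clearly. That is possible and cannot be checked here, so no effect on actual implant decisions is shown. The protocol text should still agree with itself.

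A reader might also infer that the threshold decides who counts as SNS-treated under Aim D. The documents do not say so. Sections 5.3 and 8.3 group participants by treatment-order combination after they choose an added treatment. Section 4.3.2 places the SNS initiation visit at the temporary-lead procedure, before any decision on a permanent implant. Section 2.2.3 itself objects to reporting only permanently implanted patients.

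**Conclusion.** The point holds as a wording defect: one implant threshold is expressed on two scales, and the literal form of one sentence conflicts with its neighbor.

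Two broader conclusions are tempting and unsupported. One is that the sentences give opposite decisions for every outcome other than exactly 50%; opposite decisions arise only for reductions above 0% and below 50%, and only on the literal reading. The other is that all of the roughly 40 SNS choosers face opposite decisions; on the protocol's own figures that number is at most about 4 to 12, while the 28 to 36 who meet the reduction criterion would, apart from any at exactly 50%, fall in the coverage gap.

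These counts assume that the two added-treatment options are equally popular, as section 5.4 does, and that the failure rate quoted in section 2.2.3 carries over to this trial's non-responders.

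The consequences stop at optional SNS after 3 months, the exploratory combination analyses, and the descriptive safety and cost summaries for those participants. The 3-month primary outcomes and their power are unaffected, and 3-month non-responders remain non-responders in the long-term efficacy analysis. This is a minor point, worth correcting because of what the sentence governs.

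**What to change.** The sponsor should reconcile the two sentences in section 3.0 item 4 with each other and with section 2.2.3, so that a single threshold on a single scale (percent of baseline or percent reduction) is stated throughout. Which clinical threshold applies is for the sponsor to state; this review takes no position on it. Any SNS procedure document should be checked against the reconciled text, and the second-injection wording in section 3.0 item 3 and section 6.3 can be reconciled at the same time.

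The cost for SNS is a one-sentence correction that can go into the next amendment and its IRB review. It changes no sample size, analysis or data collection. If participants have already had test stimulation, the sponsor should confirm which reading the sites applied, so that the combination results can be described accurately.
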